#### 7 Study Device Management

#### 7.1 Subject Compliance Monitoring

#### 7.1.1 $\mu$ Cor wear time

 $\mu$ Cor wear time will assessed throughout the study period. Wear time will be monitored by the sponsor based on the daily data transmissions from the  $\mu$ Cor device. It is anticipated that the wear time with  $\mu$ Cor system will be over 70% through the study period. For subjects who show early signs of non-compliance, the sponsor will inform the study coordinators, who will then make phone-calls to encourage subjects to continue wear the  $\mu$ Cor system. In addition, the study coordinators with the support of sponsor's technical support will try to trouble shoot and alleviate the reasons for subject's non-compliance.

#### 7.2 Dispensing, Storage and Return

#### 7.2.1 Dispensing of Study Device

The sponsor will ship sufficient  $\mu$ Cor devices and other study-related supplies to each site. The site will be responsible for safe storage of the devices. The Investigator will be responsible for recording the receipt of the  $\mu$ Cor system in an appropriate device log. Similarly, devices fitted on subjects will also be logged in an appropriate device log.

#### 7.2.2 Return of Study Device

The Investigator will be responsible for ensuring all study devices are returned back to the site by the subjects in a timely manner. During the study, the study coordinator must ship these returned devices to the sponsor within 10 working days. In addition, at the end of the study all unused devices must be returned to the sponsor.

#### 7.3 Device Malfunction or Defect

In case of device malfunction or defect, subjects will call the study coordinator to help debug the issue with the help of sponsor. In case the defect or malfunction cannot be resolved, new equipment will be provided to the subject.

#### 8 Statistical Plan

#### 8.1 Sample Size and Power Calculation

No sample size estimates or power calculations were performed for this feasibility study. The number of subjects for this study was determined by convenience sampling, where a maximum of 50 subjects are anticipated to participate in the study.

#### 8.2 Randomization Scheme

NA

#### 8.3 Endpoint Assessment

Study endpoints will be assessed in this feasibility study without predefined acceptance criteria.

#### 8.4 Statistical Methods

Data from all subjects in the study will be analyzed. Descriptive statistics and qualitative analysis will be used to analyze the primary, secondary, and safety endpoints.

#### 8.5 Additional Statistical Analysis

NA

#### 8.6 Handling Missing Data

NA

#### 8.7 Futility Analysis

NA

#### 9 Health Economic Evaluation

NA

# 10 Safety and Adverse Events

#### 10.1 Definitions

Adverse event are any untoward medical occurrence, unintended disease or injury or any untoward clinical signs in subjects, users, or other persons whether or not related to the study device. Serious adverse events (SAEs) are adverse events that:

- led to a death, injury or permanent impairment to a body structure or a body function
- led to a serious deterioration in health of the subject, that either resulted in a lifethreatening illness or injury, a permanent impairment of a body structure or a body

function, in-patient hospitalization or prolongation of existing hospitalization, or in medical or surgical intervention to prevent life threatening illness

• led to fetal distress, fetal death or a congenital abnormality or birth defect.

Adverse device effects (ADEs) are events related to of study device. An unanticipated ADE is any adverse effect not identified by nature, severity, or frequency prior to the study. Serious device effect are adverse device effect that has resulted in any of the consequence characteristics of a serious adverse event. Unanticipated serious adverse device effects are serious ADEs that by its nature, incidence, severity or outcome has not been identified prior to the study.

#### 10.1.1 Common Anticipated Device Effects with µCor Study Device

Anticipated events include, but are not limited to:

- 10.1.1.1 Discomfort from wearing the device.
- 10.1.1.2 Skin irritation, redness, itching, or rash.
- 10.1.1.3 Tearing of the skin if the adhesive patch is not removed carefully.
- 10.1.1.4 Allergic reaction to the hydrogel and/or Patch adhesive

#### 10.2 Recording and Reporting of Adverse Events

#### 10.2.1 Investigator Recording

Investigators must assess the seriousness of all adverse events. All serious adverse events must be recorded in the pertinent case report form (CRF). The investigator must also record if the serious adverse event is related to the study device and assess whether it is anticipated. For non-serious adverse events, the Investigators are responsible for only recording the adverse device effects and whether the ADE is anticipated or unanticipated in the pertinent case report form (CRF).

The clinical course of each event should be followed until resolution, stabilization, or until it has been determined that the study treatment or participation is not the cause. Serious adverse device effects that are still ongoing at the end of the study period must be followed up to determine the final outcome. Any serious adverse device effects that occur after the study period should be recorded.

The minimum initial information to be captured in the subject's source document concerning the adverse device effect includes:

- Study identifier
- Study Center
- Subject number
- Device model and serial number
- A description of the event
- Date of onset

- Investigator assessment of the association between the event and study treatment
- Current status
- Whether study treatment was discontinued
- Whether the event is serious and reason for classification as serious

#### 10.2.2 Reporting of Adverse Events

The following events are considered as reportable events per MEDDEV 2.7/3 revision 3 guidelines:

- any serious adverse event,
- any device deficiency that might have led to a serious adverse event if:
  - 1. suitable action had not been taken or
  - 2. intervention had not been made or
  - 3. if circumstances had been less fortunate
- new findings/updates in relation to already reported events

Investigators are to report all reportable events to the sponsor immediately, but no later than 3 calendar days after the investigational site study personnel's awareness of the event.

Reportable event are to be reported by the sponsor of the clinical investigation to all the National Competent Authorities (NCAs) where the clinical investigation has commenced. The sponsor must report to the NCAs:

- immediately, but no later than 2 calendar days of becoming aware of all reportable events that indicate an imminent risk of death, serious injury, or serious illness and that requires prompt remedial action for subjects
- immediately, but no later than 7 calendar days of becoming aware of other reportable events or new findings or updates to it.

#### 10.3 Protocol Deviations

Deviations from the protocol must receive both Sponsor and the investigator's Ethics Committee approval before they are initiated. Any protocol deviations initiated without Sponsor and the investigator's Ethics Committee approval that may affect the scientific soundness of the study, or affect the rights, safety, or welfare of study subjects, must be reported to the Sponsor and to the investigator's Ethics Committee as soon as a possible.

# 11 Administrative Responsibilities

#### 11.1 Sponsor

ZOLL Services LLC, the Sponsor, is responsible for study administration as well as providing devices and related materials for the study. The Sponsor will select appropriate investigators, assure collection of investigator agreements, assure IRB approval of the protocol, and monitor informed consent records.

The Sponsor will designate appropriately trained and qualified individuals to monitor the investigation. These individuals will verify the adherence to procedures specified in the protocol, and verify maintenance of required subject and data records.

#### 11.2 Investigators

The Investigators are responsible for obtaining and maintaining ethics approval of the study protocol. The Investigators are responsible for obtaining patient consent, and maintaining Informed Consent Forms and Case Report Forms for each subject. All forms must be signed by the Investigator or by the Investigator's designee. If the Investigators designate an individual to sign these forms, written notification must be provided to the Sponsor. The Investigators are responsible for maintaining records of study protocol deviations and amendments and all correspondence relating to the study. The Sponsor will provide an Investigator Notebook to serve as a study reference and regulatory binder. At the conclusion of the study, the Investigators will provide a summary report to the Sponsor and the reviewing Ethics Committee.

#### 11.3 Data Coordination Center (DCC)

ZOLL Services LLC, the Sponsor, will be the acting DCC. The DCC has the responsibility for clinical data coordination.

#### 11.4 Steering Committee

There is no steering committee for this study.

#### 11.5 Data Safety Monitoring Board (DSMB)

The study will not be monitored by an independent Data Safety Monitoring Board (DSMB). ZOLL Services LLC, the Sponsor, will be the acting DSMB. They will periodically review all aspects of the trial, including all adverse events, to ensure the safety of the participants.

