#### 1.1 Background

Mobile cardiac telemetry (MCT) allows for ambulatory monitoring of electrocardiograph (ECG) signal continuously. When a cardiac event occurs, the MCT system instantaneously transmits the data to a monitoring center, where the data is analyzed live and a report is sent to the patient's physician for diagnosis and therapy management. Previous studies have shown that use of MCT, instead of a Holter or event monitor, leads to better outcomes with regard to diagnostic yield, management of arrhythmias through the use antiarrhythmic drugs, and cost savings in the hospital for cardiac procedures. 4

Given the patient management capabilities of the MCT system, ZOLL has developed a novel radiofrequency (RF) based  $\mu\text{Cor}$  Heart Failure and Arrhythmia Management System ( $\mu\text{Cor}$  system). The system records ECG and heart rate through 2 electrodes and respiration rate, activity, and posture through a tri-axial accelerometer. Thoracic impedance, a measure of lung fluid, is estimated using low-power electromagnetic pulses at radio frequencies of 0.5-2.5GHz. The  $\mu\text{Cor}$  system continuously records and transmits ECG and accelerometer data to the monitoring center. RF data are recorded periodically according to a predefined schedule. Physiological parameters such as thoracic impedance, heart rate, respiration rate, activity, and posture are extracted from the recorded data by dedicated software at the monitoring center. Certified technicians at the monitoring center review received data and prepare clinical reports to the prescribing physician. Because the  $\mu\text{Cor}$  system has not yet been tested in a real-world setting, the purpose of this study is to observe the feasibility of the novel  $\mu\text{Cor}$  system to remotely monitor patients in a real-world, ambulatory setting.

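### The sponsor is to review all adverse events, but sites need record a non-serious event as an adverse event only if they attribute it to the device

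*Combined protocol and SAP*

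**What the plan says.** Four places in the combined protocol and SAP bear on this.

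- **11.5 (DSMB).** There is no independent board; "the Sponsor, will be the acting DSMB". On the scope of the review it says: "They will periodically review all aspects of the trial, including all adverse events, to ensure the safety of the participants."
- **10.1 (Definitions).** An adverse event is any untoward occurrence, "whether or not related to the study device". An adverse device effect is the subset related to the device.
- **10.2.1 (Investigator Recording).** Serious events all go on the CRF, with relatedness noted. Then: "For non-serious adverse events, the Investigators are responsible for only recording the adverse device effects", together with whether each effect was anticipated.
- **6.2.5 (End of study follow-up).** Coordinators collect any adverse events at the last visit. No relatedness limit is stated.

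The safety objective (2.3) and safety endpoint (3.4) cover device-related adverse events and all serious adverse events.

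**The concern.** The review promised in 11.5 is wider than the data that 10.2.1 requires. For non-serious events, attribution by the site decides whether an adverse-event entry is required at all. An event attributed to the device is recorded, and that attribution can later be questioned. An event put down to another cause need not be recorded as an adverse event, so that attribution cannot be questioned from adverse-event data. Errors of attribution can be corrected in one direction only, and the direction that cannot be corrected lowers the device-related count.

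This matters more here than it would for an established device. Section 1.1 says the "system has not yet been tested in a real-world setting", and 1.3 gives no clinical data to date. The list of anticipated effects in 10.1.1 is expressly not exhaustive. An effect missing from that list is one that a site has less reason to connect with the device, and one that a review across sites is meant to pick up.

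**Working it through.** The plan states no figure on this point: 8.1 has no power calculation, and no adverse-event or misattribution rate appears anywhere. The check is therefore a comparison of the rules.

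**Step 1: what each kind of event leaves behind.** All rows are adverse events under 10.1 and so fall within the wording of 11.5.

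| Event | Adverse-event CRF entry required by 10.2.1? | Other record made without a relatedness filter |
|---|---|---|
| Serious, related or not | Yes | Reported to the sponsor under 10.2.2 |
| Non-serious, attributed to device | Yes | Not needed |
| Non-serious, considered unrelated: skin | No | Diary grade 0 to 3 (3.2.6, 12.1, Appendix A) |
| Non-serious, considered unrelated: arrhythmia or heart failure symptom | No | Phase II diary (3.1, 6.2.2); weekly call (2.1.6) |
| Non-serious, considered unrelated: led to emergency or unplanned visit, or change in cardiac medication | No | Weekly call (2.1.6) |
| Non-serious, considered unrelated: anything else | No | None required before the end-of-study collection in 6.2.5 |

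**Step 2: does another section close the gap?**

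- 10.2.2 does not. Reportable events are serious events, certain device deficiencies, and updates to events already reported.
- 12.1 does not. Its list of data points includes skin condition and new symptoms but has no adverse-event item.
- Table I in 6.5 does not. It has no adverse-event row.
- 6.2.5 conflicts with 10.2.1 rather than completing it. It is also framed around the 90-day visit or the subject's own decision to stop. The day-30 visit in 6.2.3, where phase I subjects return their devices, does not mention adverse events.

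**Step 3: do the diary and call data reach the safety review as adverse events?** No section says that they are assessed for relatedness, and none specifically routes them into the 11.5 review.

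**Step 4: effect on the 3.4 endpoint.** Let N be the number of non-serious events truly caused by the device and m the share that sites put down to other causes. The required CRF entries then hold N × (1 − m) of them. With m = 0 nothing is lost; with any m above 0 the count is low by N × m. The documents give neither N nor m.

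**The case against.** The strongest reply is that the recording scope is deliberate and consistent: 2.3, 3.4 and 10.2.1 all confine non-serious events to device-related ones, and only 11.5 and 6.2.5 are worded more loosely. Section 13 describes the device as non-invasive and of non-significant risk, so limited capture is defensible, and rewording two sections would remove the contradiction. This stands as far as consistency goes. It does not give the sponsor the means to revisit attribution, which is what the review in 11.5 would need.

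A second reply is that much is recorded anyway. A reader might infer that unrelated non-serious events leave no trace, or that no safety review exists for them. The documents do not support either reading:

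- Skin effects, which make up most of the anticipated effects in 10.1.1, are graded regardless of cause.
- Phase II symptoms are logged, on a form with an open field for other symptoms, and 12.3.2 treats diaries as source documents.
- Weekly calls capture clinically actionable events.
- 11.5 speaks of all aspects of the trial, and the sponsor is also the data coordinating center (11.3).
- The CRFs are a separate document not available here, and 10.2.1 sets a minimum without forbidding further entries.

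All of this narrows the point. It does not remove it, because none of these records is required to be assessed as an adverse event.

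Third, 10.2.1 has events followed until participation is found not to be the cause, which suggests that follow-up can start before attribution is settled. That is fair, but it does not add a recording duty for non-serious events then considered unrelated.

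**Conclusion.** The point holds in a limited form. Sections 11.5, 10.2.1 and 6.2.5 state different scopes for non-serious adverse events, and the recording rule does not deliver the review that 11.5 describes. The consequence is twofold: relatedness of non-serious events considered unrelated cannot be re-assessed from adverse-event data, and any under-attribution lowers the device-related count in 3.4. The complete gap is confined to non-serious events outside the skin grades, symptom diaries and weekly-call items. It is widest among the six phase I volunteers, for whom the protocol text calls for no symptom log.

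The size of the bias cannot be estimated. A reader might try to infer it from how few patients each site sees (44 patients over the maximum of 8 sites averages 44 / 8 = 5.5). That shows how thinly cases may be spread, not how often a site misattributes one, and with fewer sites the average rises. It should not be offered as a magnitude.

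The conclusion assumes that the separate CRF document follows 10.2.1 as written. If it already collects all adverse events, only the protocol text needs aligning.

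**What to change.** **Preferred.** In 10.2.1, require every non-serious adverse event to be entered on the adverse-event CRF with term, onset, outcome and relatedness category. Leave the 3.4 endpoint as it is by applying relatedness at analysis, and show non-serious events considered unrelated in one descriptive table. Align 6.2.5 with the same rule, including for phase I subjects who finish at day 30. Section 11.5 then needs no change.

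**If the restriction is kept.** Narrow 11.5 and 6.2.5 to serious adverse events and adverse device effects, and state in 11.5 that diary skin grades, symptom logs and weekly-call data form part of the sponsor's periodic safety review. This makes the text consistent but still does not let attribution be revisited for events outside those records.

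**Cost.** The preferred change takes a few sentences and adds some adverse-event entries for at most 50 subjects over 30 to 90 days. Subjects are already called weekly, so no further visits are needed.

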# 12 Data Collection and Management Plan

#### 12.1 Data Collection

The following data points will be collected during the study:

- Patient demographics
- Clinical history, including comorbidities
- Medication and dosage
- Device placement, subject training, device data transmission, and monitoring report receipt during the initial device fitting at the physician's office
- Wear time data
- Accuracy and repeatability of device placement
- Skin condition
- Number of data transmissions from device to remote servers
- Timing of monitoring reports to physicians
- Emergency room visits
- Physician visits
- New arrhythmia and HF symptoms
- All-cause and HF hospitalizations

Survival information

#### 12.2 Data Coordinating Center (DCC)

NA

#### 12.3 Data Handling and Record Keeping

#### 12.3.1 Case Report Forms (CRFs)

Data will be collected at the investigational sites using the electronic data capture (EDC) system ClindexLIVE (Fortress Medical Systems, LLC, Hopkins, MN). Electronic Case Report Forms (eCRFs) will be implemented within ClindexLIVE by ZOLL's Clinical Data Manager. Data will be entered at the investigational sites by trained staff. Entered data will be reviewed by the site investigator, who will affirm its accuracy and completeness by electronic sign-off. The capability of the ClindexLIVE system to implement edit checks during the data entry process (front end edit checks) will be utilized to generate queries automatically at the time of data entry when malformed, out-of-bounds or missing required data are detected. All data gueries, whether automatically or manually generated, will be communicated to and cleared by investigational site staff via ClindexLIVE, which provides a full featured query handling capability. Center staff will either correct or affirm all data that generates queries, which keeps all data processing in the hands of the investigational sites, not ZOLL. ZOLL's Clinical Data Manager and Clinical Scientist will review all cleared queries for appropriateness. A final comprehensive review of all of the data will occur at the conclusion of the trial. All queries will be resolved and all eCRFs will be electronically signed by appropriate center investigators prior to database lock.

Paper CRFs will be available for recording patient data in the event that the data entry system becomes unavailable because of a technical failure. All paper CRFs will be completed by the same trained personnel who would otherwise use the EDC system. Appropriately completed and signed paper CRFs may become the source data, and will be retained by the individual centers. Once the EDC system again becomes available, the patient data will be transcribed from the paper form into the EDC system by the same person who completed the paper form.

The paper CRFs for this study are documented under 90D0167 CRF.

#### 12.3.2 Source Documents

Source data is all information, original records of clinical findings, observations, or other activities in a clinical trial necessary for the reconstruction and evaluation of the trial. Source data are contained in source documents. Examples of these original documents, and data records include: hospital records, clinical and office charts, laboratory notes, memoranda, subjects' diaries or evaluation checklists, pharmacy dispensing records, recorded data from automated instruments, copies or transcriptions certified after verification as being accurate and complete, microfiches, photographic negatives, microfilm or magnetic media, x-rays, subject files, and records kept at the pharmacy, at the laboratories, and at medico-technical departments involved in the clinical trial.

#### 12.3.3 Electronic Data Capture (EDC) System

The ClindexLIVE software system was selected for use for this clinical trial because of its full-featured capability, security features, and wide acceptance within the clinical trial industry. ZOLL's Clinical Data Manager, in consultation with ZOLL's Clinical Scientist, will implement the set of eCRFs in Clindex LIVE, and develop a set of test data. User acceptance testing at ZOLL will demonstrate accurate and complete functioning of all data and edit check elements prior to rollout of the EDC system to the investigational sites. The clinical database will be hosted at Fortress Medical Systems, LLC, using redundant on- and off-site resources, throughout the data collection process. Data access (both entry and review) will be controlled by user ID and password restricted user authentication. Only users who have been appropriately trained will be permitted to perform data entry. Once entered by site personnel, data will be reviewed by the site investigator who will have eCRF signature authority. The ClindexLIVE system features a fully documented audit trail on all CRF data modified after first pass entry and automatic audit trail on all data changes. Individual report level security allows for a customized report environment for individual users and sites, so that users and sites may access only the data which they have entered into the system. The ClindexLIVE system has been independently certified to be 21 CFR Part 11 compliant.

